8.4.2 UNANTICIPATED PROBLEMS REPORTING

Unanticipated problems will immediately be reported to the IRB. The Principal Investigator will consult with the IRB to determine if it is necessary to suspend data collection for modification of the protocol or other changes. Other changes will include a corrective plan and measures to prevent reoccurrence. Resumption shall be based on the concurrence of the Principal Investigator, the IRB and any other relevant parties. We will report such events within 48 hours to the NIA unless they are also SAEs. We will also report unanticipated problems, as defined above, to OHRP using [contact] within two weeks of the event.

Note: Per NIA policy, all deaths require expedited reporting (usually within 24 hours of study's knowledge of death). The report of death should be submitted to the NIA Program Officer. When SAEs occur that are unanticipated (i.e., not listed in the Data and Safety Monitoring Plan) and that are related to the intervention, they should be reported to the NIA Program Officer within 48 hours of study's knowledge of SAE.

8.4.3 REPORTING UNANTICIPATED PROBLEMS TO PARTICIPANTS

N/A

9 STATISTICAL CONSIDERATIONS

9.1 STATISTICAL HYPOTHESES

We hypothesize that the impact of the treatments on our primary endpoints will be positive overall (due to the increased work and income), but that the Stable Income will have the largest treatment effects, the Predictable Volatility arm the next largest, and the Unpredictable Instability arm the least (though still positive relative to the control). Alternatively, our null hypothesis is that there will be no difference among the experimental arms.

9.2 SAMPLE SIZE DETERMINATION

Given IPAs' performance on similar previous surveys during the lean season (when respondents are relatively available), we assume a uniform 5% attrition across all arms.

We will recruit 2,267 participants. 1,067 will be assigned to the Unpredictable Instability arm and 400 to each one of the other three study arms. About 37.5% of the Unpredictable Instability arm (i.e., 400 individuals) are expected to have Neutral 4-period schedules, such that the estimation of the effect of ex-ante income uncertainty corresponds to a randomized controlled trial with a sample size of 760 (95% of 800) equally split between "treatment" and "control". For a two-tailed test with 0.05 significance level and 0.8 power, the minimum detectable effect (MDE) is 0.2 of a standard deviation (SD) for each primary outcome (calculations done in Stata). These effect sizes are consistent with those found in the literature on the effects of cash transfers in low-income settings (e.g., Haushofer & Shapiro, 2016 & 2018; McIntosh & Zeitlin, 2020). Similarly, the MDE for the effect of predictable income volatility is also 0.2 SD. The estimation of the effect of income risk, which corresponds to RCT where 72.7% of the 1,394 (95% of 1,467) participants are assigned to the treatment condition, has an MDE of 0.17 SD. The estimation of the effect of income realizations has an MDE of 0.19 SD if those with unlucky and lucky schedules are grouped together and of 0.23 SD if they are each compared separately to those with Neutral schedules. For panel data analyses, standard errors will be clustered at the individual level (the unit of randomization) (Abadie et al. 2017). These are conservative estimates that consider data from the follow-up survey only; they ignore that we will have baseline measures of all outcomes of interest, which should substantially reduce MDEs, and that we will have repeated measures of most outcomes. In addition to an index of mental health, given the rapid evolution of multiple hypothesis testing techniques, will we use state of the art techniques to adjust for multiple hypothesis testing.

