1.3 SCHEDULE OF ACTIVITIES

Day		Day o	Day	Day	Day	Day	Day	Day 80-100	Day 98-
-30			10-14	24-	38-	52-	70-		102
to -1				28	42	56	74		
				En	d of peri	iod			4 weeks
		Baseline	2	3	4	5	6		later
	Demographics	Full							
	Economic	Full	Short	Short	Short	Short	Full		Short
	measures								
ц	Psychological	Full	Short	Short	Short	Short	Full		Short
tio	wellbeing								
Iza	(Depression,								
m	Anxiety,								
Idc	Stress via								
an	cortisol and							Qualitative	
1 pi	self report,							debriefs for	
an	worry,							subset of	
ng	subjective-							participants	
in:	wellbeing)								~1
ree	Physical	Full					Full		Short
Sc	health (blood								
	pressure,								
	dietary								
	diversity and								
	sumciency,								
	weight)	37	37	37	37	37	37	37	37
	Adverse event	X	Х	X	X	X	Х	X	Х
	reporting								

Participants will be surveyed at Baseline, the end of every 2-week period, and 4 weeks after the end of the active intervention. The Baseline and post period 6 survey are in person and more extensive (lasting roughly 2-2.5 hours). All remaining surveys are telephonic and last roughly 20-30 minutes. Treated participants will additionally be offered work throughout Days 0-74 according to their experimental arm and randomized draws.

Ethical reviews (detailed in section 1) have been completed. We anticipate beginning the pilot study in late April 2024 and the full study in April of 2025. Within each of these studies, the timeline will proceed as detailed in the table above. Following the completion of the RCT in the summer of 2025, we will assay the cortisol samples, analyze the data, write manuscripts, and disseminate results in 2025-2026.

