Randomization will be done using statistical software for the treatment assignments and a process of drawing sealed envelopes for the period-by-period realizations in the Unpredictable Instability arm (to increase trust in the randomization process). The Control, Stable, Predictable Volatility arms will each have 400 participants. The Unpredictable Instability arm is overweighted with 1,067 participants, as the analysis of this arm will be disaggregated depending on the draws realized by each participant. The participant will learn of their study arm assignment after consent and the baseline survey, but prior to the beginning of the first 2-week period. The PIs and associated staff under their direction will generate the randomization code and output, with the exception of the period-by-period draws for the Unpredictable Instability participants which will occur in the field.

Unpredictable Instability participants will realize their draw for the next period in the five days between the time when the work for the prior period is completed and the work for the next period begins. This randomization is assured to be truly random via the following procedure:

- The field officer arrives at the participant's house with two sealed envelopes. One contains a "high" draw and the other a "low" draw for the period, as indicated by a work calendar. Both have the participant's ID number on the outside of the reverse (sealed) side of the envelope.
- The participant selects and opens one envelope
- The field officer photographs the calendar from the open envelope in the same frame as the sealed envelope with the same participant ID. This ensures that we can verify which envelope was opened first, and hence the draw of the participant for that period.
- The participant then opens the second envelope to verify that it held the other type of calendar/draw.

While we do not anticipate having randomization errors, should they occur, we will drop those participants from the study.

Each participant will be enrolled for 6 2-week periods. In addition, they will respond to an eligibility survey roughly 2-4 weeks prior to enrollment and complete a follow-up survey 1 month following the end of the active study period.

All participants will be enrolled from a single site surrounding Tamale, Ghana.

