Effect of Ex-Ante Income Uncertainty. We will estimate *ex-ante* income uncertainty by comparing Unpredictable Instability and Predictable Instability participants with *identical earnings profiles over time.* E.g., we will compare the Unpredictable Instability participants to the Predictable Instability participants. They had identical profiles over the first 4 periods. But, the Predictable Instability participant knew these income swings in advance while the Unpredictable Instability participant did not. The comparison is internally valid because the earnings profile for the Unpredictable Instability participant is randomly determined. To compensate for using a subsample of the arm, more individuals will be assigned to it.

Effect of Income	Table 4: Group Comparisons and the Effects They Estimate			
estimate the effect of	Comparison of	Estimates Effect of		
income realizations	Stable Income to Control	Level of Income		
(what actually happened) by	Predictable Instability to Stable Income	Predictable Instability		
comparing	Unpredictable Instability to Predictable Instability	Unpredictable Instability		
Unpredictable Instability	Unpredictable Instability and Predictable Instability with Identical Earnings Profiles over Time	Ex-Ante Income Uncertainty		
participants who by chance end up with	Unpredictable Instability w/ Diff. Income Realizations	Ex-Post Income Realizations		

different income realizations.

Justification of the Control: For our study we will randomly select individuals from those determined to be eligible to serve as an internal control group for comparison as there may be significant time trends in this population given the progression through the lean season. These individuals will be surveyed following the same timeline as all other participants, but not participate in the work program. Given that our sample density is less than five percent in any selected village, we do not anticipate spillovers from randomly sampled individuals in treatment arms to or from individuals in the control arm.

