6 STUDY INTERVENTION(S) OR EXPERIMENTAL MANIPULATION(S)

6.1 STUDY INTERVENTION(S) OR EXPERIMENTAL MANIPULATION(S) ADMINISTRATION

6.1.1 STUDY INTERVENTION OR EXPERIMENTAL MANIPULATION DESCRIPTION

The poor are known to suffer disproportionally from poor mental and physical health. Many causes for these disparities have been considered, including low income. Yet, poor families' incomes are not only low, but also often unstable and unpredictable (Collins et al. 2009). Income instability creates uncertainty about whether they will be able to safeguard their future wellbeing: Will they have enough money to put food on the table? To pay for rent? To pay for a doctor's visit? (Jolliffe and Ziliak 2008; Bhattacharya et al. 2004) The allostatic load framework posits that, if uncertainty (of any type) is not resolved, prolonged activation of physiological stress responses will cause "wear and tear" on the body, heightening risks of cardiovascular disease and of agerelated metabolic diseases, promoting cognitive decline and dementia, and accelerating cellular aging (Peters et al. 2017). Income instability could therefore increase the rate of aging among the poor and contribute to disparities in physical and psychological health.

In order to parse the impacts of volatility and uncertainty on mental health, we must vary both the variance in income and what is know about the expected path of income among participants while holding constant the mean expected income.

To accomplish this, all participants are enrolled in the study for 6 two-week "periods" (3 months) and a short follow-up survey one month after the end of the active study period. During the study period participants are randomly divided into the following four groups.

1) *The Control Arm.* The Control arm will not be hired by the cash-for-work program but will be surveyed.

2) *The Stable Income Arm*. The Stable Income arm will work the same number of hours (36) and earn the same amount (108 GHS) every period.

3) *The Predictable Instability Arm*. The hours and earnings of the Predictable Instability arm will vary over time. In three periods, the participant will work longer hours (60) and will earn more (180 GHS). In the remaining three periods, she will work fewer hours (12) and will earn less (36 GHS). Crucially, she will be able to predict all swings in her study earnings in the future—i.e., she will know her hours and earnings in each future period.

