6.3 MEASURES TO MINIMIZE BIAS: RANDOMIZATION AND BLINDING

We will recruit 2,267 participants, randomly assigning 400 to the Control, 400 to the Stable Income, 400 to the Predictable Volatility, and 1,067 to the Unpredictable Instability arm. Among those in the Unpredictable Instability arm, we expect 1/3 to end the study with the same average earnings as those in the Stable or Predictable volatility arm. Roughly 1/3 will earn more overall and roughly 1/3 will earn less overall, given the randomized draws. Participants are not (and cannot be) blind to their condition. The randomization will be conducted using Stata or R following the completion of the screening process. Because not all individuals selected via screening will consent, we will identify "backup" participants in each wave of enrollment to reach our target enrollments. We will stratify the randomization within village to improve power.

2,267 Participants					
400 Control	400 Stable Income	400 Predictable Volatility	1,067 Unpredictable Instability		

The period-by-period randomization for the amount of work received by each participant in the Unpredictable Instability arm will follow the protocol described in Section 4.1.

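### Section 9.2 sizes the ex-ante uncertainty contrast on four-period schedules, but for outcomes read after period 6 the matched group is about 333 women, not 400 (MDE 0.213 SD, not 0.203 SD)

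*Combined protocol and SAP*

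**What the plan says.** Section 9.2 states: "About 37.5% of the Unpredictable Instability arm (i.e., 400 individuals) are expected to have Neutral 4-period schedules". With 400 Predictable women and 5% attrition this becomes 760 analysed in two equal groups, and "the minimum detectable effect (MDE) is 0.2 of a standard deviation (SD) for each primary outcome". Of its MDEs the section says: "These are conservative estimates that consider data from the follow-up survey only". The same paragraph gives MDEs for the effect of income realizations: 0.19 SD with lucky and unlucky schedules grouped, and 0.23 SD with each compared separately with Neutral schedules.

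Section 4.1 says: "Each participant will be enrolled for 6 2-week periods". Under 6.1.1, each Unpredictable draw is high (180 GHS) or low (36 GHS) with probability one half, and a Predictable woman has three high and three low periods. Section 4.2 defines the contrast by identical earnings profiles over time and adds an example: "They had identical profiles over the first 4 periods". Section 9.4.1 requires the payment schedule to be held constant but names no window. Section 6.3, describing the end of the trial, says: "we expect 1/3 to end the study with the same average earnings as those in the Stable or Predictable volatility arm".

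On timing, Section 1.3 says: "The Baseline and post period 6 survey are in person and more extensive". Its table lists the physical health measures (blood pressure, diet, weight) at baseline, after period 6 and, in short form, four weeks later. Blood pressure and diet are primary endpoints.

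**The concern.** The sample size counts women whose schedule is balanced after four draws, yet the MDE is claimed for every primary outcome from a follow-up survey. Whether that means the endline or the survey four weeks later, all six draws are over by then. Two more draws after period 4 break the balance for half of the women counted. For blood pressure and diet there is no earlier post-baseline reading to which a four-period match could apply.

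This contrast separates uncertainty from realised income, which belongs to the first secondary objective. Sections 4.1 and 4.2 also give the use of a subsample as the reason for enlarging the Unpredictable arm to 1,067. For end-of-study outcomes, the group that 9.2 counts is not the group with the same realised offers.

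**Working it through.** **Inputs.** Two-sided alpha 0.05, power 0.80, 5% attrition, 1,067 Unpredictable and 400 Predictable women (9.2); six draws at one half (4.1, 6.1.1); three high and three low Predictable periods (6.1.1). Outcomes are in SD units with no baseline adjustment, as in 9.2.

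**Formulas.** Balanced share after k draws = C(k, k/2)/2^k. MDE = (1.960 + 0.842) × √(1/n1 + 1/n2).

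**The plan's figure.**
- C(4,2)/2^4 = 6/16 = 37.5%; 1,067 × 0.375 = 400.1. Conversely, 400/0.375 = 1,066.7, the arm size.
- 0.95 × 400 = 380 per group, 760 in all.
- MDE(380, 380) = 0.203 SD; power at 0.20 SD is 78.7%.

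The stated 0.2 SD is reproduced.

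**The 400 women after two more draws.**

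| High–low after six | Total offered | Women |
|---|---|---|
| 3–3 | 3×180 + 3×36 = 648 GHS (the Predictable total) | 0.50 × 400 ≈ 200 |
| 4–2 | 4×180 + 2×36 = 792 GHS | 0.25 × 400 ≈ 100 |
| 2–4 | 2×180 + 4×36 = 504 GHS | 0.25 × 400 ≈ 100 |

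**Six-period basis, matched on total offered earnings.**
- C(6,3)/2^6 = 20/64 = 31.25%; 1,067 × 0.3125 = 333.4 women. About 200 of them were balanced after four draws; the other 133 were 3–1 or 1–3.
- Analysed: 0.95 × 333.4 = 316.8, against 380; total 696.8.
- MDE(316.8, 380) = 0.213 SD; power at 0.20 SD is 74.8%.

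**Same order instead of same total.** If the Predictable arm uses m of the 20 possible 3–3 orders, 1,067 × m/64 Unpredictable women share an order with some Predictable woman. The maximum, at m = 20, is 333, and 0.213 SD then assumes that the orders are used evenly. The documents do not give m. As an illustration only, m = 12 used evenly gives 200 women (190 analysed) and 0.249 SD.

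**Realisation MDEs in the same paragraph.** Analysed Unpredictable women: 0.95 × 1,067 = 1,013.65.
- Four periods: 380 Neutral and 25% (253) in each outer group gives 0.190 grouped and 0.227 separately. This reproduces 0.19 and 0.23, provided lucky and unlucky mean exactly three or one high draws.
- Six periods, everyone above or below balance: (1 − 0.3125)/2 = 34.375% each. 317 v 697 grouped gives 0.190; 317 v 348 separately gives 0.217. (This 697 is the two outer groups combined; it matches the 697 above by coincidence.)
- Six periods, only 4–2 and 2–4 counted (15/64 each): 0.203 and 0.240.

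**Baseline adjustment.** The MDE is multiplied by √(1 − r²). To bring 0.2132 back to 0.2032 needs r = √(1 − (0.2032/0.2132)²) = 0.30; to reach 0.200 needs r = 0.35. The documents give no r, so these are assumptions.

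**The case against.** The strongest reply is that the four-period window is deliberate. Section 9.2 labels it, 4.2 uses it, and the figure is correct on that basis. This stands as far as it goes: there is no slip in the calculation. But 4.2 gives the window only as an example, and it cannot serve outcomes with no post-baseline reading before the end of period 6.

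A reader might also infer that 6.3 contradicts 9.2, one third against 37.5%. It does not. Section 6.3 describes earnings at the end of the study and rounds 31.25%, just as it rounds the 34.4% above and below to roughly one third each. The two sections describe different windows.

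A third reply is that the consequence is small and that 9.2 leaves out baseline and repeated measures. This also stands for the size of the effect. Repeated measures help little for blood pressure and diet, which have at most two post-baseline readings.

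Fourth, 333 matches on total earnings and ignores order, so it may not meet the identical-profile definition in 4.2. That is right, and the figure has to be labelled accordingly.

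Finally, 9.4.1 promises a pre-analysis plan after the pilot. The window could be set there, but that would not correct the figure that 9.2 now states.

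**Conclusion.** For outcomes at the end of period 6 and at follow-up, 9.2 states a sample size that the design does not deliver. The group with equal total offered earnings is about 333 women rather than 400. The unadjusted MDE moves from 0.203 to 0.213 SD, and power at 0.20 SD falls by about 4 points. This rests on the plan's own draws, arm sizes and attrition, and on matching by total offered earnings. If matching must be on order, 333 is the most favourable case.

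The point is minor. Both MDEs round to 0.2, full-arm contrasts are unaffected, and a moderate baseline correlation would offset the loss.

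Two stronger readings are not supported. One is that the arm must grow: keeping 400 balanced women over six periods would take 400/0.3125 = 1,280, but a change of 0.01 SD does not call for it. The other is that the stated MDE is also too optimistic for depression and anxiety at period 4. That depends on Predictable calendars which the documents do not list. With the 20 orders used evenly (an assumption), keeping only women balanced after four periods leaves 240 of the 400 Predictable women and 0.235 SD, whereas matching every woman on her own earnings history gives 0.174 SD. The direction is therefore open.

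**What to change.** In 9.2:

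- For outcomes at the end of period 6 and at follow-up, replace 37.5% / 400 / 760 / 0.2 SD with 31.25% / about 333 / 697 (317 v 380) / 0.21 SD unadjusted.
- Label this as a match on total six-period earnings. If 4.2 or 9.4.1 means the same order, say that it is the most favourable case and recompute n and MDE from the Predictable calendars actually used.
- Restate the realisation MDEs on the same basis: about 0.19 SD grouped (317 v 697) and about 0.22 SD separately (317 v 348). Define lucky and unlucky, since these figures count every woman above or below balance.
- Keep any four-period match, with its own MDE, only for outcomes measured at the end of period 4 (depression, anxiety). Compute its n from the Predictable calendars that are balanced at that point.

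In 4.2, tie the four-period example to those outcomes. The one third in 6.3 can stay as a rounded figure.

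The cost is wording and a few numbers, with a slightly less favourable unadjusted MDE for end-of-study outcomes. Enrolment does not change.

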9.3 POPULATIONS FOR ANALYSES

The primary analysis will be intention-to-treat (all randomized participants).

9.4 STATISTICAL ANALYSES

9.4.1 GENERAL APPROACH

To study the effects of uncertainty, we will compare the outcomes of participants assigned to the Unpredictable Instability arm to the outcomes of participants assigned to the Predictable Instability arm, while holding the payment schedule constant. Similarly, to study the effects of predictable income volatility, we will compare the outcomes of participants assigned to the Predictable Instability arm to the outcomes of participants assigned to the Stable Income arm. Finally, we will estimate the effects of a stable income by comparing the outcomes of participants assigned to the Control arm.

For each of the individual outcomes, the primary regression model will be:

$$Y_{it} = \lambda_0 + \sum_{\{k=1\}}^3 \lambda_1^k T_i^k + \lambda_2 X_i + \lambda_3 Y_{i0} + \gamma_t + \epsilon_{it}.$$

where *i* indexes the individual; Y_i is individual *i*'s outcome in the post-treatment period *t*; T_i^k is an indicator for treatment arm k; X_i is a vector of individual-level controls (e.g., age); Y_{i0} is the dependent variable at baseline; and; ϵ_i is the error term. Period fixed effects (γ_t) are also included to control for period effects. The analysis considers treatment assignment as the independent variable, regardless of compliance (i.e., intent-to-treat). We utilize an ANCOVA regression model. Standard errors are clustered by individual. λ_1 are the key coefficients of interest and can be interpreted as the causal effect of each treatment relative to the control group. Additional comparisons between treatments will be conducted to parse the impacts of predictable and unpredictable volatility. Also, to study if outcomes fluctuate together with income, we will compare participants from a given arm with different current study earnings (but who had identical earnings in the past). Given the rapid evolution of multiple hypothesis testing.

A pre-analysis plan will be registered after the pilot but prior to the main study with any updates to this analysis plan based on learnings from the pilot.

